### **6.4. Interim Analysis**

No interim analysis is planned for this study.

## **7. STATISTICAL ANALYSES**

### **7.1. Subject Disposition**

The number of subjects included in each study population will be summarized by treatment regimen and overall. Subjects excluded from the safety, ITT, or mITT populations will be listed.

The frequency counts and percentages of subjects screened, enrolled, completed, and/or withdrawn from the study, as well as the reason for withdrawal from study will be summarized by treatment regimen and overall.

A listing of disposition data will be provided. Screen failure reasons will also be listed. In addition, listing for inclusion/exclusion criteria will also be presented.

### **7.2. Protocol Deviations**

Protocol deviations will be summarized by deviation classification (major/minor), and by treatment regimen and overall. A listing of all protocol deviations will be presented.

### **7.3. Demographics and Baseline Characteristics**

Demographics and baseline characteristics will be summarized by treatment regimen and overall using the Safety Population. Age, height (at Screening), body weight (at Screening), BMI in kg/m^2 (at Screening) and time since last menstrual period will be summarized as continuous variables using descriptive statistics.

Gender, race and ethnicity will be summarized as categorical variables using frequency counts and percentages.

Refer to [Table 19](#) for descriptions of age categories.

The following baseline characteristics will be summarized using frequency counts and percentages:

- CR-PCSS cellulite severity ratings for thigh and buttock at screening (mean and SD will also be provided).
- Hexsel CSS Section D (laxity, flaccidity or sagging of skin) scores at screening (mean and SD will also be provided).
- Skin category based on Fitzpatrick scale assessment.
- Report of substance use
  - Alcohol use (Never, Current or Former).
  - Tobacco use (Never, Current or Former).
  - Illegal Drug use (Never, Current or Former).

All demographic and baseline characteristics will be presented in subject listings.

### **7.4. Medical and Surgical History**

Medical history will be coded using MedDRA. Medical and surgical history data will not be summarized; however, a subject listing will be provided.

### **7.5. Cellulite History**

Cellulite history will be summarized by treatment regimen and overall using frequency counts and percentages which will include:

- Age (years) at cellulite symptom onset (summarized descriptively).
- Prior treatments for cellulite including liposuction, laser, massage, radiofrequency, drug, mesotherapy, cream, other, or none. Subjects can report more than 1 prior cellulite treatment.
- Number of prior cellulite treatments (0, 1, 2, or ≥3).
- Time (years) since most recent cellulite treatment (summarized descriptively).

Refer to [Table 19](#) for computation of “age at cellulite onset” and “time since last cellulite treatment.” Cellulite history will be listed.

## **7.6. Prior/Concomitant Medications and Procedures**

Prior and concomitant medications will be summarized by treatment regimen and overall using frequency counts and percentages by active ingredient within each ATC, with ATC and active ingredients ordered alphabetically. Prior and concomitant procedures (non-drug therapies) will be summarized by treatment regimen and overall using frequency counts and percentages with name of the procedures ordered alphabetically. Multiple uses of the same medication/procedure by a subject will be counted only once.

A subject listing of medications indicating prior and concomitant medications and procedures will be provided. Similarly, a separate listing of medications and procedures for cellulite will also be presented.

## **7.7. Efficacy Analyses**

Efficacy parameters will be summarized for each treatment area (buttock or thigh), treatment regimen and overall using the mITT Population.

### **7.7.1. Primary Efficacy Endpoint**

#### **7.7.1.1. One-level I-GAIS Responders**

The 1-level I-GAIS responders will be summarized by treatment regimen and overall using frequency counts, proportion and corresponding 95% CI based on the Clopper-Pearson method for 1-level I-GAIS responders at Day 180 and Last for each treatment area and either buttock or either thigh.

The definition of a one-level responder is provided in Section [4.6.1.2](#).

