### **3.5. Pre-Randomization of Samples into Four Groups**

All subjects must have the following:

- a cellulite score of 2 (mild) or 3 (moderate) on the CR-PCSS assessment and
- a dermal laxity score of 2 (moderate) or 3 (severe) on the Hexsel CSS Subsection D assessment.

Once a subject's treatment areas are classified to the defined categories, pre-randomization will be performed with the interactive response technology (IRT) cohort management module. Pre-randomization will be used to manage recruitment such that approximately equivalent numbers of subjects are enrolled for treatment of buttocks vs thighs, mild vs moderate cellulite, and moderate vs severe dermal laxity.

This pre-randomization process will be used in an attempt to fill the desired categories as shown in Table 3 below.

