**Table 3: Intended Distribution of Subject Treatment Area Characteristics and Locations**

Criteria	CR-PCSS 2 (mild cellulite)	CR-PCSS 3 (moderate cellulite)
Hexsel CSS Subsection D2 (moderate laxity)	8 Buttocks	8 Buttocks
	8 Thighs	8 Thighs
Hexsel CSS Subsection D3 (severe laxity)	8 Buttocks	8 Buttocks
	8 Thighs	8 Thighs
Total	32 Treatment Areas	32 Treatment Areas

Note: A total of 32 subjects are expected to contribute a total of 64 treatment areas. Each subject’s 2 treatment areas may be allocated to different categories according to the severity of cellulite and severity of dermal laxity.

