### **7.7.2. Secondary Efficacy Endpoints**

#### **7.7.2.1. One-level I-GAIS Responders by Visit**

The 1-level I-GAIS responders will also be summarized by treatment regimen and overall using frequency counts, proportion and corresponding 95% CI based on the Clopper-Pearson method for 1-level I-GAIS responders at Day 28, Day 56, Day 84, Day 112, Day 140, and Last for each treatment area and either buttock or either thigh.

Additionally, I-GAIS ratings will also be summarized at Day 28, Day 56, Day 84, Day 112, Day 140, Day 180, and Last for each treatment area.

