#### **7.7.2.2. One-level S-GAIS Responders by Visit**

The 1-level S-GAIS responders will also be summarized by treatment regimen and overall using frequency counts, proportion and corresponding 95% CI based on the Clopper-Pearson method for 1-level S-GAIS responders at Day 28, Day 56, Day 84, Day 112, Day 140, Day 180 and Last for each treatment area and for either buttock or either thigh.

The definition of a one-level responder is provided in Section [4.6.2.2](#).

Additionally, S-GAIS ratings will also be summarized at Day 28, Day 56, Day 84, Day 112, Day 140, Day 180 and Last for each treatment area.

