**7.7.2.4. Change from baseline in Hexsel CSS Subsection D Score by Visit**

The observed and change from baseline (Day 1) to each analysis visit (Day 28, Day 56, Day 84, Day 112, Day 140, Day 180, and Last) in Hexsel CSS Subsection D severity score will be summarized by treatment area and severity grades.

A listing of Hexsel CSS Subsection score will be provided.

**7.7.3.** [REDACTED]

**7.7.3.1.** [REDACTED]

[REDACTED]

**7.7.3.2.** [REDACTED]

[REDACTED]

[REDACTED]

[REDACTED]

[REDACTED]

[REDACTED]

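### Should the I-GAIS and S-GAIS responder summaries be broken down by the cellulite and laxity grades used to manage recruitment?

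*SAP*

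**What the plan says.** SAP 3.5 uses the IRT cohort module so that "approximately equivalent numbers of subjects are enrolled for treatment of buttocks vs thighs, mild vs moderate cellulite, and moderate vs severe dermal laxity". SAP Table 3 (protocol Table 2) sets an intended 8 areas in each of 8 cells. Its note adds that a subject's "2 treatment areas may be allocated to different categories according to the severity of cellulite and severity of dermal laxity".

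The efficacy layout in SAP 7.7 is: "Efficacy parameters will be summarized for each treatment area (buttock or thigh), treatment regimen and overall using the mITT Population". The primary summary in 7.7.1.1 covers "1-level I-GAIS responders at Day 180 and Last for each treatment area and either buttock or either thigh". The visit summaries follow the same pattern: "1-level I-GAIS responders at Day 28, Day 56, Day 84, Day 112, Day 140, and Last for each treatment area" in 7.7.2.1 and "1-level S-GAIS responders at Day 28, Day 56, Day 84, Day 112, Day 140, Day 180 and Last for each treatment area" in 7.7.2.2, each also for either buttock or either thigh. None of these names a CR-PCSS or Hexsel D grade as a breakdown, and protocol 9.3.1.1 to 9.3.1.3 add none.

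The grades appear in two other readable places. SAP 7.3 tabulates screening CR-PCSS and Hexsel D scores by regimen and overall. SAP 7.7.2.4 says that the observed score and change "in Hexsel CSS Subsection D severity score will be summarized by treatment area and severity grades". That concerns the laxity endpoint, not GAIS response, and does not say whether the grades are baseline or observed. SAP 7.7.3 and the exploratory objectives are redacted.

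**The concern.** Three factors steer enrolment, but only region gets its own rows in the responder tables. Laxity is the reason for the study: protocol 2.1 says earlier CCH studies left out women with significant laxity. A reader could therefore expect to see whether severe laxity responds less well than moderate laxity.

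The overall responder rate is also an average over a grade mix that the quota aims for but does not guarantee. If response differs by grade and the achieved mix drifts from the intended one, the overall rate moves with it, and the responder tables alone would not show why. At stake would be the interpretation of the primary proportion and a lost chance to describe response by severity.

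**Working it through.** **1. Reproduce the plan's figures.** SAP Table 3: 2 CR-PCSS grades × 2 Hexsel D grades × 2 regions × 8 areas = 64 areas. That is 32 per CR-PCSS grade, likewise 32 per Hexsel D grade, and 64/2 = 32 women. This matches the table and its note. With the 24 evaluable women of protocol 4.1 there are 48 areas, or 24 per grade if split evenly.

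**2. Is grade a factor that the analysis must carry?**

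- SAP 3.1 gives the purpose of the pre-randomization step as securing the desired range of participants; SAP 3.5 describes it as managing recruitment.
- SAP 3.6.2 and protocol 6.1 describe 1:1 assignment through IRT and name no strata.
- SAP Table 1 defines the primary endpoint as one responder proportion at Day 180.
- SAP 3.6.1 justifies the sample size as an initial evaluation in one population spanning both cellulite grades and both laxity grades.
- Protocol 2.1 proposes benefit for moderate to severe laxity taken together. It does not contrast the two grades.

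These passages support including both grades. None asks for them to be compared.

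**3. What can a reader already see?** The achieved grade mix is in SAP 7.3, by regimen and overall. Listings of all eCRF and derived data (SAP 6.1) hold the grade and the I-GAIS rating of each area for about 32 women.

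**4. How far could the mix move the reported rate?** The inputs are assumptions: area response 75% at a 50:50 laxity mix, and a 20-point gap (85% moderate, 65% severe).

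Pooled area rate = 75 + 20/2 − 20 × severe share. At 25% severe it is 80%; at 75% severe it is 70%, a swing of 10 points.

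The primary endpoint, however, is response on either side. With both areas of a woman in one grade and within-woman correlation ρ, the either-side rate is 1 − [(1−p)² + ρp(1−p)].

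| ρ | Moderate (p = 0.85) | Severe (p = 0.65) | 25% severe | 75% severe | Swing (points) |
|---|---|---|---|---|---|
| 0 | 97.75% | 87.75% | 95.25% | 90.25% | 5.0 |
| 0.7 | 88.83% | 71.83% | 84.58% | 76.08% | 8.5 |

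If 75% is instead the either-side rate, the swing is about 9 to 10 points. All of this supposes a mix as uneven as 25:75 although IRT is steering towards equal numbers. At any mix, the reported rate is still the correct proportion for the women enrolled.

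**5. Could a table by grade show the gap?** Wald 95% half-width for one grade = 1.96 × √[p(1−p)(1+ρ)/n], both areas of a woman in one grade:

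- n = 24, p = 0.75, ρ = 0: 1.96 × √(0.1875/24) = 17.3 points.
- n = 24, p = 0.75, ρ = 0.7: 17.3 × √1.7 = 22.6 points.
- n = 24, either-side rate fixed at 75% (p = 0.500 at ρ = 0; p = 0.6853 at ρ = 0.7): 20.0 and 24.2 points.

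For the difference between two grades of equal size, multiply by √2: 24.5 to 34.3 points with 24 areas per grade. With all 32 women (32 areas per grade) the range is 21.2 to 29.7. The assumed 20-point gap lies inside every one of these.

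The exception is one area in each grade for every woman. The half-width is then 1.96 × √[2p(1−p)(1−ρ)/24], which at ρ = 0.7 is 13.4 points (p = 0.75) or 14.4 points (p = 0.6853). Nothing in the plan leads one to expect that every woman will be discordant.

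Full cells would say less still. For 6 responders of 8 areas, treated as independent, the Clopper-Pearson interval is 34.9% to 96.8%.

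**The case for a change.** The best case for the table is that it is cheap. SAP 4.6.1.2 already defines a responder per area, the data are collected, and no amendment is needed. A prespecified descriptive table is harder to select or over-read than one made after the results are known. Precision alone does not rule it out either: the SAP already plans intervals by regimen for single areas, where the ideal number is 8 women per region and regimen.

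Much of that stands. It is true that the readable responder summaries carry no grade, and that listings allow a later tabulation without prespecifying one. The mix in SAP 7.3 is also for the Safety Population, whereas efficacy uses the mITT Population, though the two differ only by injected women without a valid I-GAIS afterwards.

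These points show that the table would be harmless and mildly informative. They do not show that the plan fails without it. No readable objective asks for response by grade and no estimate or interval would change. Because a woman's two areas can differ in grade, the either-side endpoint may have no single grade to be classified by. The table would therefore have to be a separate area-level analysis, not a breakdown of the primary result.

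**Conclusion.** The concern does not hold. The missing breakdown is real in the readable text, but recruitment grades are not analysis factors here, and the plan followed as written answers the question it sets: one responder proportion in the combined population, with the achieved mix reported beside it.

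Under the assumed 20-point gap, a shift in the laxity mix from 25% to 75% severe would move the either-side rate by 5.0 to 8.5 points (about 9 to 10 if 75% is the either-side rate). A table by grade would have a half-width of 21.2 to 34.3 points for the difference unless women's two areas usually fell in different grades. The rates, the gap and the correlations of 0 to 0.7 are assumptions; the documents give none.

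The conclusion rests on the readable text. Redacted SAP 7.7.3 may already contain such a table, which would only strengthen it. A descriptive table by grade is a matter of preference, and no change to the plan is needed.

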### **7.7.2. Secondary Efficacy Endpoints**

#### **7.7.2.1. One-level I-GAIS Responders by Visit**

The 1-level I-GAIS responders will also be summarized by treatment regimen and overall using frequency counts, proportion and corresponding 95% CI based on the Clopper-Pearson method for 1-level I-GAIS responders at Day 28, Day 56, Day 84, Day 112, Day 140, and Last for each treatment area and either buttock or either thigh.

Additionally, I-GAIS ratings will also be summarized at Day 28, Day 56, Day 84, Day 112, Day 140, Day 180, and Last for each treatment area.

#### **7.7.2.2. One-level S-GAIS Responders by Visit**

The 1-level S-GAIS responders will also be summarized by treatment regimen and overall using frequency counts, proportion and corresponding 95% CI based on the Clopper-Pearson method for 1-level S-GAIS responders at Day 28, Day 56, Day 84, Day 112, Day 140, Day 180 and Last for each treatment area and for either buttock or either thigh.

The definition of a one-level responder is provided in Section [4.6.2.2](#).

Additionally, S-GAIS ratings will also be summarized at Day 28, Day 56, Day 84, Day 112, Day 140, Day 180 and Last for each treatment area.

**7.7.2.3. Change from baseline in Body-Q -Appraisal of Cellulite Total Score by Visit**

The observed and change from baseline (Day 1) in Body-Q Appraisal of cellulite total score will be summarized at Day 180 and Last by treatment regimen and overall using descriptive statistics.

In addition to Body-Q Appraisal of Cellulite score, change from baseline and subjects that improved (change from baseline  $\geq +1$ ) for each of individual 11 items will be summarized for treated buttock or thigh subjects at Day 180 and Last using frequency counts and percentages with mean and SD.

A listing of Body-Q™ ratings will be provided.

**7.7.2.4. Change from baseline in Hexsel CSS Subsection D Score by Visit**

The observed and change from baseline (Day 1) to each analysis visit (Day 28, Day 56, Day 84, Day 112, Day 140, Day 180, and Last) in Hexsel CSS Subsection D severity score will be summarized by treatment area and severity grades.

A listing of Hexsel CSS Subsection score will be provided.

**7.7.3.** [REDACTED]

**7.7.3.1.** [REDACTED]

[REDACTED]

**7.7.3.2.** [REDACTED]

[REDACTED]

[REDACTED]

[REDACTED]

[REDACTED]

[REDACTED]

## **7.8. Safety Analyses**

Safety data will be summarized by treatment regimen and overall using the Safety Population.

### **7.8.1. Study Drug Exposure**

The following will be summarized at each treatment visit by treatment regimen for each treatment region (thigh or buttock) and each treatment area (left or right) using descriptive statistics:

- Total number of injections given.
- Number of sub-area under each treatment area treated.
- Number of additional sub-area under each treatment area treated.
- Number of treatment region treated.
- Average number of injections per sub-area under each treatment area.
- Duration of exposure (refer to [Table 19](#) for computation of exposure duration).

The number of subjects treated at each treatment visit will be summarized using frequency counts and percentages by treatment area for each treatment region and treatment regimen.

A subject listing of drug exposure information will be provided.

### **7.8.2. Adverse Events**

All AE summary tables will include only TEAEs, unless otherwise specified. TEAEs will be summarized by SOC and PT. A subject will only be counted once per SOC and PT.

For TEAEs by severity grade (mild, moderate, severe), if a subject has multiple events occurring in the same SOC or same PT, then the event with the maximum intensity (ie, severe) will be counted.

For TEAEs by relationship to study drug, if a subject has multiple events occurring in the same SOC or same PT, the event with the highest association (ie, related) to study drug will be summarized.

An overall summary of TEAEs and TEAEs related to study drug will be presented and will include:

- Total number of TEAEs reported.
- Total number of TEAEs reported by severity.
- Total number of TEAEs of special interest.
- Subjects with any TEAE.
- Subjects with any TEAE of special interest.
- Subjects with any serious TEAE.
- Subjects with any severe TEAE.
- Subjects with no severe TEAEs, but at least one moderate TEAE.
- Subjects with no severe TEAEs, but at least one mild TEAE.
- Subjects with any TEAEs leading to drug interruption/discontinuation.

- Subjects with any TEAEs leading to withdrawal from study.
- Subjects with any TEAEs resulting in death.

The following summary tables will be presented by SOC and PT:

- All TEAEs.
- Study drug related TEAEs.
- TEAEs by severity.
- Study drug related TEAEs by severity.
- TEAEs by treatment session.
- Duration of study drug related TEAEs (1 – 7 days, 8 – 14 days, 15 – 21 days, >21 days).
- Serious TEAEs.
- TEAEs of special interest.
- TEAEs of special interest by severity.

The most common non-serious TEAEs by order of frequency (most frequent, 2nd most frequent, and 3rd most frequent) will be summarized by PT. The most common non-serious AEs are those with any PT that at least 5% of the subjects reported at least once.

The following listings will be presented by subject:

- All AEs.
- Fatal AEs.
- Non-fatal serious AEs.
- Non-fatal non-serious AEs leading to study discontinuation.
- Non-fatal non-serious AEs resulting in drug interruption/withdrawn.

Refer to [Table 19](#) for computation of duration of AEs.

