**Table 4: Study Treatment**

Regimen Name	A	B
Injection Technique	Uniform 0.1-mL 1-Aliquot GRID	Uniform 0.3-mL 2-Aliquot GRID
Product Name	CCH	CCH
Number of Subjects	N = 16 (8 buttocks and 8 thighs) a	N = 16 (8 buttocks and 8 thighs) a
Injection Volume (mL) × Aliquot(s) = Total Injection Volume	0.1 mL × 1 = 0.1 mL	0.3 mL × 2 = 0.6 mL
Concentration (mg/mL)	[REDACTED]	[REDACTED]
Maximum CCH Dose/ Treatment Area	1.68 mg (0.84 mg per buttock or thigh)	1.68 mg (0.84 mg per buttock or thigh)
Maximum Injection Volume/Visit	[REDACTED]	[REDACTED]
Maximum Number of Injection Sites/Subject/Visit	[REDACTED]	[REDACTED]
Cumulative CCH Dose 3 Treatment Visits 6 Treatment Visits	5.04 mg 10.08 mg	5.04 mg 10.08 mg

a Number of subjects shown for buttocks and thighs treatment represents the ideal distribution.

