#### **4.7.1.2. Intensity of Adverse Events**

Intensity (or severity) of AEs will be graded as “Mild”, “Moderate” or “Severe”. For AEs with missing severity, the most severe assessment will be imputed for analyses, following worst case principle. If the intensity of an AE changes, then the most severe intensity during the continuous episode will be recorded.

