### **6.3. Handling of Missing Data**

Subjects who withdraw from the study after the initiation of the study drug will not be replaced and available data for these subjects until the point of withdrawal will be summarized.

The missing baseline assessment will not be imputed.

For categorical variables with missing values, a category documenting the frequency of missing values will be displayed in the summary tables.

For Body Q- Appraisal of Cellulite, if missing data at a visit is less than 50% of the scale's items, the mean of the completed items multiplied by 11 will be used to determine total score. Also, if the missing data at a visit is more than 50% then for that subject raw sum score will be considered as missing.

There will be no imputation of missing values for safety data, however missing relationship between AE and study drug will be considered as related to study drug following worst case principle. Missing severity of an AE will be summarized as a severe AE. Duration of the AE is classified in the '>21 Days' category if an AE is ongoing for more than 21 days by the last visit of the subject in the study.

Immunogenicity samples with a positive titer value will undergo a log transformation for analyses. Samples with titer level less than 10 will be assigned or imputed as a log transformed titer of 1 for analyses.

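### The mild row of the overall TEAE summary does not exclude moderate events, so some subjects are counted in two severity rows

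*SAP*

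**What the plan says.** SAP section 7.8.2 plans an overall summary for all TEAEs and for those related to study drug. Besides the total row, "Subjects with any TEAE", it lists three consecutive subject-level rows by severity:

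- The severe row is worded "Subjects with any severe TEAE", with no exclusion.
- The moderate row removes the grade above it: "Subjects with no severe TEAEs, but at least one moderate TEAE".
- The mild row carries the same single exclusion as the moderate row: "Subjects with no severe TEAEs, but at least one mild TEAE".

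Every TEAE ends up with one of the three grades. Section 4.7.1.2 states: "For AEs with missing severity, the most severe assessment will be imputed for analyses, following worst case principle". Section 6.3 agrees: "Missing severity of an AE will be summarized as a severe AE". On presentation, section 7.8 says: "Safety data will be summarized by treatment regimen and overall using the Safety Population".

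The protocol does not define these rows. Its section 9.3.2 refers to the SAP for the detail of the safety analyses, and section 9.3.2.1 gives only a general description of the AE summaries.

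**The concern.** The severe and moderate rows read as the first two steps of a worst-grade classification: severe first, then moderate among those with no severe event. The natural third step is mild among those with neither. The mild row instead repeats the exclusion used for the moderate row.

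A reader may take the mild row as the number of subjects whose worst event was mild, and it will overstate that number whenever the overlap is above zero. Safety and tolerability is a secondary objective, and the table is shown by regimen and overall, so the error would appear in each column. The overlap pattern is plausible here. Subjects may have up to six treatment sessions in two areas, and protocol sections 2.2 and 2.3 describe earlier events as mainly injection-site reactions of mild to moderate grade.

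**Working it through.** **Inputs.** The row definitions come from SAP 7.8.2. The planned numbers are 32 subjects (SAP 3.1) and 16 per regimen (SAP Table 4). The documents state no figure for these rows, so there is none to reproduce.

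**Step 1: pass every severity pattern through the rows.** For one subject, let S, M and L mean at least one severe, moderate or mild TEAE. As written:

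- severe row = S
- moderate row = not S, and M
- mild row = not S, and L

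| S | M | L | Severe | Moderate | Mild as written | Rows as written | Rows if mild also requires not M |
|---|---|---|---|---|---|---|---|
| no | no | yes | 0 | 0 | 1 | 1 | 1 |
| no | yes | no | 0 | 1 | 0 | 1 | 1 |
| no | yes | yes | 0 | 1 | 1 | **2** | 1 |
| yes | no | no | 1 | 0 | 0 | 1 | 1 |
| yes | no | yes | 1 | 0 | 0 | 1 | 1 |
| yes | yes | no | 1 | 0 | 0 | 1 | 1 |
| yes | yes | yes | 1 | 0 | 0 | 1 | 1 |

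Six of the seven patterns with any TEAE fall in one row. The pattern with no severe but both moderate and mild events falls in two. With the added exclusion, all seven fall in exactly one row.

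**Step 2: look for another rule that removes the overlap.** The maximum-intensity rule in 7.8.2 applies to several events within one SOC or PT, in the by-severity tables. The rule in 4.7.1.2 takes the worst grade within one continuous episode of one event. Neither gives a subject a single worst grade across different events. Missing severity counts as severe, so there is no fourth category that could account for a mismatch with the total row.

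**Step 3: size.** Let k be the number of subjects with no severe TEAE and both a moderate and a mild one. Then:

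- mild row as written = (worst grade mild) + k
- sum of the three rows = (any TEAE) + k

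Each such subject adds 1/32 = 3.1 points overall and 1/16 = 6.25 points within a regimen of 16.

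**Step 4: illustration with assumed counts.** Take 32 subjects: 3 with any severe TEAE, 15 with worst grade moderate and 12 with mild events only, giving 3 + 15 + 12 = 30 with any TEAE. Vary how many of the 15 also had a mild event:

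| k (of 15) | Mild row as written | Percent of 32 | Sum of three rows | Any TEAE |
|---|---|---|---|---|
| 0 | 12 + 0 = 12 | 37.5% | 3 + 15 + 12 = 30 | 30 |
| 5 | 12 + 5 = 17 | 53.1% | 3 + 15 + 17 = 35 | 30 |
| 10 | 12 + 10 = 22 | 68.8% | 3 + 15 + 22 = 40 | 30 |
| 15 | 12 + 15 = 27 | 84.4% | 3 + 15 + 27 = 45 | 30 |

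The worst-grade-mild count is 12 in every line.

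**Step 5: a second illustration with assumed, independent per-subject probabilities.** Expected k = 32 × (1 − P(S)) × P(M) × P(L).

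- Severe 10%, moderate 20%, mild 80%: 32 × 0.90 × 0.20 × 0.80 = 4.6
- Severe 5%, moderate 30%, mild 90%: 32 × 0.95 × 0.30 × 0.90 = 8.2
- Severe 10%, moderate 50%, mild 90%: 32 × 0.90 × 0.50 × 0.90 = 13.0

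**Step 6: recovery.** In the first illustration, any TEAE minus severe minus moderate = 30 − 3 − 15 = 12, so the intended count can be rebuilt from the same table.

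**The case against.** Nothing in the SAP says that the three rows must be mutually exclusive or sum to the total. Other rows in the same list overlap by design, such as serious events, events of special interest and events leading to withdrawal. The mild row is true to its own label, and a careful reader would not take it as a worst-grade count. The intended number can be recovered by subtraction, the by-severity tables and AE listings are also planned, and the study is exploratory and not powered to compare the regimens. The illustrated sizes rest on assumed counts.

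Much of this stands, and it is why the point is minor. The worst-grade intent is an inference. It is a strong one: if simple counts of any event at each grade were meant, the moderate row would have no reason to exclude severe events. The mild row as worded matches neither reading. The planned by-severity tables are by SOC and PT, and the SAP does not say that they carry a subject-level worst-grade line.

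A further objection concerns the related-TEAE summary. If the added exclusion were applied there to all TEAEs, a subject with a related mild event and an unrelated moderate one would fall in no row. The natural scope of that table is related events only, but the revised text should say so.

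**Conclusion.** The concern holds. As written, a subject with no severe TEAE and both a moderate and a mild TEAE is counted in the moderate row and again in the mild row, and no other rule in the SAP prevents this. The excess in the mild row is exactly the number of such subjects. That number cannot be derived from the documents. The per-subject steps of 3.1 and 6.25 points assume the planned 32 and 16, and the actual Safety Population may differ.

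The conclusion that this is an error, not an unusual but deliberate row, rests on reading the moderate row as one step of a worst-grade breakdown. The consequence is small: one descriptive row and its study-drug-related counterpart. The severe and moderate rows, the SOC and PT severity tables and all efficacy results are unaffected.

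**What to change.** In SAP 7.8.2, reword the mild row so that it counts subjects with neither a severe nor a moderate TEAE and at least one mild TEAE. Make the same change in the study-drug-related summary, and state that in that table all the severity conditions refer to related TEAEs. The three rows then sum to the number of subjects with any TEAE, or any related TEAE, which also gives the programmer a simple check. The cost is one phrase in the SAP and the matching table shells, with no new data.
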